4.3.2 Implementation Hypotheses

1. There will be higher fidelity to the critical action checklist relating to the provision of ED-initiated BUP with referral for ongoing MAT in the IF evaluation period compared with the baseline evaluation period
2. A greater rate of patients in the IF evaluation period will receive an appointment with an opioid provider/program upon ED discharge compared with the baseline evaluation period
3. A greater number of providers will undergo DATA 2000 training in the IF evaluation period compared with the baseline evaluation period
4. A greater number of clinicians will provide ED-initiated BUP with referral for ongoing MAT in the IF evaluation period compared with the baseline evaluation period
5. ED provider readiness and preparedness ruler scores will reflect a greater readiness and preparedness for provision of BUP and referral for ongoing MAT in the IF evaluation period compared with the baseline evaluation period
6. ED ORCA scores will reflect a greater organizational readiness to change with respect to provision of ED-initiated BUP in the IF evaluation period compared with the baseline evaluation period
7. Community opioid treatment provider/program provider readiness and preparedness ruler scores to continue MAT for patients with OUD who have received ED-initiated BUP will be greater in the IF evaluation period compared with the baseline evaluation period
8. Community opioid treatment provider/program ORCA scores relating to receiving patients with OUD who have received ED-initiated BUP will be greater in the IF evaluation period compared with the baseline evaluation period.

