12.14.3 Secondary Implementation Outcomes

- Fidelity (as measured by the check list score) to a critical action checklist relating to the provision of ED-initiated BUP with referral for ongoing MAT in eligible patients will be compared in the IF evaluation period to the baseline evaluation period. This will be done using standard models including mixed models, or other appropriate methodology.

- Rates of enrolled patients with OUD receiving an appointment for opioid treatment provider/program upon ED discharge. The IF evaluation period will be compared to the baseline evaluation period using the model described for the primary analysis in section 12.14.1.
- Number of ED providers receiving DATA 2000 training will be compared between IF evaluation period and baseline evaluation period using appropriate methodology. Permutation tests will be considered for this analysis.
- Number of clinicians providing ED-initiated BUP with referral for ongoing MAT will be compared in the IF evaluation period to the baseline evaluation period using count models. Models considered will be Poisson, zero-inflated Poisson, negative binomial and zero-inflated negative binomial. An offset will be considered for how long the provider has been trained.
- ED provider readiness and preparedness ruler scores to initiate BUP and provide referral for ongoing MAT will be compared between IF evaluation period and baseline evaluation period. This will be done using standard models including mixed models or other appropriate methodology. If the data do not follow a Gaussian distribution a modified Wilcoxon test ⁵⁸ will be used.
- ED Organizational Readiness to Change Assessment (ORCA) scores relating to ED-initiated BUP with referral for ongoing MAT will be compared between IF evaluation period and baseline evaluation period. This will be done using standard models including mixed models or other appropriate methodology. If the data do not follow a Gaussian distribution a modified Wilcoxon test will be used.
- Community opioid treatment provider/program readiness and preparedness ruler scores to continue MAT for patients with OUD who have received ED-initiated BUP will be compared between IF evaluation period and baseline evaluation period. This will be done using standard models including mixed models or other appropriate methodology. If the data do not follow a Gaussian distribution a modified Wilcoxon test will be used.

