7.6 Definition of Secondary Outcome Measures

7.6.1 Secondary Implementation Outcomes

1. Fidelity to the Critical Action Checklist relating to the provision of ED-initiated BUP with referral for ongoing MAT as captured by the CAC form. For the binary variable, if all critical actions were completed for a given participant the variable will be coded 1 versus 0 if at least one critical action was not completed. The count variable will be defined as the number of critical actions completed per given participant.
2. Rates of enrolled patients with OUD receiving an appointment for opioid treatment provider/program upon ED discharge as recorded on EDR form. The variable will be coded 1 if YES is endorsed on “Did the patient receive a referral to opioid use disorder (OUD) treatment?” and 0 if the answer is NO.
3. Number of ED providers receiving DATA 2000 training as reported on ICH form: The outcome is the number of participants who endorsed YES on the question “In the past year, did you attend or complete a DATA 2000 training on buprenorphine prescribing that would allow you to obtain a DEA waiver?”.
4. Number of clinicians providing ED-initiated BUP with referral for ongoing MAT as reported in ICH form.
5. ED provider readiness and preparedness ruler scores to initiate BUP and provide referral for ongoing MAT as reported on RRL form: The outcome will be scored from the following

questions: “On a scale from 0 to 10, how prepared are you to provide ED-initiated buprenorphine with referral for ongoing medication assisted treatment (MAT) for the treatment of opioid use disorder, where 0 equals “not prepared at all” and 10 equals “totally prepared?” and “On a scale from 0 to 10, how ready are you to provide ED-initiated buprenorphine with referral for ongoing MAT for the treatment of opioid use disorder, where 0 equals “not ready at all” and 10 equals “totally ready?”.

6. ED ORCA scores relating to ED-initiated BUP with referral for ongoing MAT (OE1 and OE2 form). The score will be dichotomized, as was done in Hawk et al.⁵, where scores in the first four quintiles were categorized as less ready, and scores in the upper quintile is considered most ready.
7. Community opioid treatment provider/program readiness and preparedness ruler scores to continue MAT for patients with OUD who have received ED-initiated BUP (RRL form).

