8. Community opioid treatment provider/program ORCA scores relating to receiving patients with OUD who have received ED-initiated BUP (OC1 and OC2 form).

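### The SAP splits the ED ORCA score at a top quintile of unstated origin where the protocol compares the score itself; under roughly normal scores this costs about half the information

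*SAP*

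**What the plan says.** SAP 7.6.1, item 6, defines the ED ORCA outcome: "The score will be dichotomized", following an earlier published study. The lower four fifths form one group, while "scores in the upper quintile is considered most ready". No source distribution for the quintiles is given, and nothing says whether one cut serves all three survey waves.

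The protocol treats the same outcome as a score. Section 4.3.2 expects that "ED ORCA scores will reflect a greater organizational readiness to change with respect to provision of ED-initiated BUP in the IF evaluation period", relative to baseline. Section 12.14.3 says that ED "ORCA) scores relating to ED-initiated BUP with referral for ongoing MAT will be compared between IF evaluation period and baseline evaluation period". The method there is left fairly open (mixed models among the standard models, or something else suitable), with a fallback: "If the data do not follow a Gaussian distribution a modified Wilcoxon test will be used".

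The neighbouring SAP items are handled differently. Item 8, "Community opioid treatment provider/program ORCA scores relating to receiving patients with OUD who have received ED-initiated BUP", carries no split. Nor do the readiness rulers in items 5 and 7. For the critical action checklist (item 1) the SAP defines both a binary and a count variable; for the ED ORCA it defines only the binary one. SAP 3.4 summarises ORCA scores by site, survey wave and provider type.

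**The concern.** The protocol's fallback for awkward distributions is a rank test, which keeps the ordering of the scores. A yes/no at the 80th percentile does not: movement wholly below or wholly above the cut is invisible. The secondary hypothesis that ED readiness rises would then be tested with much less power than the collected data allow, and on a different footing from the community ORCA.

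The missing definition of the cut is a second problem. A quintile is a property of some sample. Depending on which sample is used, the same data give different shares, and under one possible choice they can give no difference at all. The wave-to-wave forms make this more than a formality: protocol 11.3 omits the facilitation items from the baseline survey and adds them later, so a single cut on the full score would compare scores built from different items.

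**Working it through.** The documents give no effect size, standard deviation, power or sample size for the ORCA, so there is no figure of the plan's own to reproduce.

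**Inputs**
- Cut at the 80th percentile: SAP 7.6.1, item 6.
- Respondents: protocol 12.3 expects about 25–30 ED providers per site to be engaged. Over four sites that is 100–120; the midpoint, 110, is used. This is not a survey response count, so it is an assumption.
- Assumed, because the documents are silent: normal scores, independent respondents, shifts of 0.2–0.5 SD, two-sided 0.05.

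**Step 1: information kept by the split.** Relative to comparing means of a normal score, a cut at quantile q retains φ(z_q)² / [q(1−q)]. With q = 0.8, z = 0.8416 and φ(z) = 0.2800, this is 0.0784 / 0.16 = 0.490, so 51% is lost. A median split would retain 0.637.

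**Step 2: finite shifts.** The ratio of the n needed for 80% power (score over split) is 0.52–0.56 with a cut fixed at baseline and 0.47–0.49 with a pooled cut, for shifts of 0.2–0.5 SD. The loss is therefore 44–53%. At 0.4 SD, n per wave is 99 for the score, 182 for the baseline cut and 206 for the pooled cut.

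**Step 3: illustrative power at 110 per wave.**
- Score, 0.4 SD: 0.4 × √(110/2) = 2.966; 2.966 − 1.960 = 1.006; power 84%.
- Baseline cut, 0.4 SD: the follow-up share is 1 − Φ(0.8416 − 0.4) = 0.329 against 0.200, difference 0.1294. The null standard error is √(2 × 0.2647 × 0.7353 / 110) = 0.0595 and the alternative one is 0.0588. (0.1294 − 1.96 × 0.0595) / 0.0588 = 0.217; power 59%.
- Pooled cut, 0.4 SD: the shares become 0.145 and 0.255, difference 0.1102, with standard errors 0.0539 and 0.0534. The same formula gives 0.084; power 53%.

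| Shift | n per wave | Score | Baseline cut | Pooled cut |
|---|---|---|---|---|
| 0.3 SD | 110 | 60% | 37% | 34% |
| 0.4 SD | 100 | 81% | 55% | 50% |
| 0.4 SD | 110 | 84% | 59% | 53% |
| 0.4 SD | 120 | 87% | 62% | 57% |

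**Step 4: what the source of the quintiles does.** Simulation: 3,000 runs, 110 per period, score taken as the mean of 15 five-point items (the item count is an assumption). Shares labelled most ready, first against second period:
- Quintiles formed within each period: 19.0% v 19.0%, 19.0% v 18.9% and 19.0% v 18.6% at shifts of 0, 0.4 and 0.8 SD, with no rejections at any shift. Ties put the share slightly under 20%.
- Pooled cut at 0.4 SD: 13.8% v 24.1%, rejected in 49.5% of runs.
- Baseline cut at 0.4 SD: 19.0% v 31.9%, rejected in 58.5% of runs.
- Test on the score at 0.4 SD: rejected in 81.1% of runs.

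The discrete scores therefore behave much as the normal formulas predict.

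**The case against.** The strongest reply has four parts.

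First, this is one of eight secondary implementation outcomes. SAP section 9.0 treats secondary findings as hypothesis-generating. That stands and keeps the severity low. It does not justify a weaker test: the same section reports secondary findings only when p is well below 0.05, where power is lower than in the table.

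Second, the protocol left the method open, the SAP says it expands on the protocol, and a published categorisation is easy to interpret. The open wording concerns how scores are compared; it does not turn the score into a binary outcome. An analyst reading item 6 would take the binary variable as the outcome.

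Third, SAP 3.4 still describes ED and community scores alike. That stands. A reader might infer that a rise in ED readiness could not be seen, or that ED and community results could not be set side by side. The documents do not support either inference; only the formal ED comparison is affected.

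Fourth, a reader might infer that the result is fixed at 20% whatever happens. That follows only if quintiles are recut within each wave, which no section states. The cited study is dated 2020 in the SAP's reference list, while the last site's IF evaluation period ended in October 2020, with the last survey towards the end of that period. A cut carried over from earlier data is thus also plausible. What the text supports is narrower: the source of the cut is unstated, and one reading it does not exclude would make the test uninformative.

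**Conclusion.** The point holds as a low-severity improvement. The SAP replaces the protocol's comparison of ED ORCA scores with a top-quintile yes/no, gives only a citation for doing so, and leaves the cut undefined. The efficiency of 0.49 rests on approximate normality; the documents do not give the score distribution. The power figures also rest on an assumed shift and on about 110 independent respondents per wave, and they ignore clustering within four sites and repeat respondents. They show scale and do not predict this trial's power. No primary result, sample size or safety conclusion is touched.

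**What to change.** In SAP 7.6.1, item 6, make the formal ED ORCA comparison on the score, as in protocol 12.14.3, using the evidence and context items asked at every wave. Account for site, and for repeat respondents where responses can be linked across waves; the documents do not confirm that they can, so the provider term should be conditional on it. The site and provider terms and the restriction to common items go a little beyond the protocol text and should be written down as such. Keep the top-quintile share as a supportive or descriptive result, with one stated cut fixed from the baseline survey on those same items.

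The cost is SAP wording and an analysis of scores already collected. No new data, respondents or visits are needed.

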7.6.2 Secondary Effectiveness Outcomes

1. Self-reported days of illicit opioid use (past seven-days) as measured by TLFB method at 30 days: The following substances collected on TLFB method will be considered illicit opioid use if there is no prescription: heroin, oxycodone, hydrocodone, fentanyl, morphine, hydromorphone, meperidine, methadone, buprenorphine, oxymorphone, pentazocine, and codeine.
2. Overdose events (past 30 days) captured by participant self-report in ODE: The outcome will be scored from question 1 “On how many days in the past 30 days do you think you overdosed on opioids (you used more opioids than you should have used and were more sedated, drugged, or high than you wanted to be)?”
3. HIV risk taking behaviors (past 30 days) as captured in HST.
4. Healthcare service utilization (past 30 days).
5. Rates of illicit opioid negative urines at 30 days as captured on urine drug screen (UDS): A UDS will be considered negative for opioids if all of the following substances are negative: opiates (2000ng), oxycodone, methadone, opiates (300ng), buprenorphine and fentanyl. If a participant tests positive on the UDS for any of these substances and self-reports on TLFB that they have a prescription for any opioid, then the use will be considered licit (i.e., not illicit).

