4.3.4 Effectiveness Hypotheses (at 30-day follow-up assessment)

Patients in the IF evaluation period compared with baseline evaluation period will:

1. Report fewer days with illicit opioid use in the past 7 days
2. Experience fewer overdose events (past 30 days)
3. Report fewer HIV risk taking behaviors (past 30 days)
4. Utilize fewer inpatient OUD services (past 30 days)
5. Have greater rates of illicit opioid negative urine tests at 30 days

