8.4 Secondary Effectiveness Outcome Measures

To compare the baseline evaluation and IF evaluation periods on:

1. Self-reported days of illicit opioid use (past 7 days) measured by TLFB methods at 30 days
2. Overdose events (past 30 days) captured by participant self-report, state medical examiner records, National Death Index and review of medical records
3. HIV risk taking behaviors (past 30 days) as measured by HIV Risk Taking Behavior Score
4. Healthcare service utilization (past 30 days) measured by Health Services Utilization Form
5. Rates of illicit opioid negative urines at 30 days

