12.14.4 Effectiveness Outcomes

- The primary effectiveness outcome is defined as the rates of patient engagement in formal addiction treatment on the 30th day post enrollment. The model described in section 12.14.1 and 12.14.2 will be used to analyze this outcome.
- Self-reported days of illicit opioid use (past 7-days) as measured by TLFB methods at 30 days will be compared between IF evaluation period and baseline evaluation period using count models. Models considered will be Poisson, zero-inflated Poisson, negative binomial and zero-inflated negative binomial.

- Overdose events (past 30 days) captured by participant self-report, state medical examiner records, National Death Index and review of medical records will be compared using count models. Models considered will be Poisson, zero-inflated Poisson, negative binomial and zero-inflated negative binomial. An offset will be considered for how long a participant was in a given period if less than 30 days.
- HIV risk taking behaviors (past 30 days) as measured by HIV Risk Taking Behavior Score will be compared between IF evaluation period and baseline evaluation period. This will be done using standard models such as mixed models or other appropriate methodology. If the data do not follow a Gaussian distribution a modified Wilcoxon test will be used.
- Healthcare service utilization (past 30 days) measured by Health Services Utilization Form will be compared using count models. Models considered will be Poisson, zero-inflated Poisson, negative binomial and zero-inflated negative binomial. An offset will be considered for how long a participant was in a given period if less than 30 days.
- Rates of illicit opioid negative urines at 30 days. The IF evaluation period will be compared to the baseline evaluation period using the model described for the primary analysis in section 12.14.1.

For all secondary analyses, covariates such as sex, race and ethnicity will be considered if appropriate and feasible. Specifically, if model based approaches are used covariates will be considered. If non-parametric methods are used then the tests may be done at different covariate levels.

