All overdose events will be captured for this study. Non-fatal overdose events will be captured through participant self-report on the Overdose CRF. This information will be collected at the enrollment visit as well as all follow-up visits for the study. Fatal overdose events will be captured through state medical examiner records, National Death Index, and review of medical records. *Fatal overdose events also qualify as a reportable SAE and will, therefore, be additionally reported on the AE/SAE CRF form set. *Note: only death events that occur within the 30-day follow-up period will be recorded on the AE/SAE form set.

OTHER EVENTS

Pregnancy is not exclusionary and will not be captured as the procedures for prescribing medication is per standard of care.

Incarceration that occurs on study will be reported on the Crime and Criminal Justice case report form but will not be considered an adverse or serious adverse event.

Loss of confidentiality related to participation in this study will be monitored at the site and will be reported on the Protocol Deviation eCRF as well as reported to the IRB of record per IRB requirements.

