8.2 Overdose Events

Overdose events reported on the ODE form at the Day 30 follow-up visit will be summarized by evaluation period. A listing of overdose events report at the follow-up visit will be presented by site for each evaluation period and will include number of days the participant overdosed on opioids and the number of days the participant needed medical assistance for an opioid overdose in the past 30 days. A listing will also be created for participants enrolled who were later found to have been ineligible if any ODE data is available for them at the follow-up visit.

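### The SAP reports as overdose events a self-reported count of days that also admits over-sedation, and it leaves out the record sources that the protocol names, so fatal overdoses cannot count

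*SAP*

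**What the plan says.** Protocol 8.4 defines the outcome as "Overdose events (past 30 days) captured by participant self-report, state medical examiner records, National Death Index and review of medical records". Protocol 12.14.4 repeats the four sources and assigns Poisson or negative binomial models, with or without zero inflation. The hypothesis in Protocol 4.3.4 is that patients in the IF evaluation period have fewer overdose events than baseline patients. Protocol 14.12 divides the work by type of event: "Non-fatal overdose events will be captured through participant self-report on the Overdose CRF", while fatal overdoses come from medical examiner records, the National Death Index and medical records.

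SAP 7.6.2 item 2 narrows the source to "Overdose events (past 30 days) captured by participant self-report in ODE". It scores the outcome from question 1 of that form, "On how many days in the past 30 days do you think you overdosed on opioids", and the question explains overdose to the patient as "you used more opioids than you should have used and were more sedated, drugged, or high than you wanted to be". The SAP gives no reason for choosing this item and plans no analysis on a narrower definition.

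A narrower item is already on the form. SAP 8.2 lists, for safety, "the number of days the participant needed medical assistance for an opioid overdose in the past 30 days", and Table 35 summarises it beside question 1 by evaluation period.

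**The concern.** The label on the outcome and the quantity scored do not match, in two ways.

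First, the wording put to the patient requires no loss of consciousness, no reversal treatment and no medical care. Every participant has moderate to severe OUD, so a day of being higher than intended can score the same as a life-threatening overdose. The unit is also a day (0 to 30), so two overdoses on one day count once.

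Second, a patient who dies of an overdose cannot answer the question. With the record sources dropped, the outcome can count unwanted sedation and cannot count an overdose death.

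What is at stake is the interpretation of one secondary hypothesis. A lower rate on question 1 could reflect fewer days of over-sedation, fewer overdoses or both. A null result could hide a fall in overdoses. Neither can be resolved from the planned test.

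**Working it through.** The plan gives no overdose rate, effect size or power for this outcome, so there is no figure to reproduce. The finding rests on comparing the texts. The arithmetic only shows when over-inclusion matters.

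**Texts side by side**

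| Feature | Protocol 8.4, 12.14.4, 14.12 | SAP 7.6.2 item 2 |
|---|---|---|
| Unit | Overdose events | Days out of 30 |
| Sources | Self-report and three record sources | Self-report only |
| Fatal overdose | Captured from records | Cannot enter |
| Threshold | Not spelled out | More sedated, drugged or high than wanted is enough |

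**Illustration of attenuation**

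From the documents: about 120 patients per site per period at 4 sites, so n = 4 × 120 = 480 per period (Protocol 12.3). Assumed: 0.10 true overdoses per patient per 30 days at baseline; IF halves them; negative binomial dispersion k = 3; one-sided 5% test; site and time effects ignored. Let s be the share of question 1 days that are true overdoses and r the rate ratio for the other days.

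- Observed rate ratio: RR = 0.5s + r(1 − s)
- Baseline mean of question 1: m1 = 0.10/s; IF mean: m2 = m1 × RR
- SE of log RR: √[(1/m1 + k)/480 + (1/m2 + k)/480]
- Power: Φ(|ln RR|/SE − 1.645)

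Benchmark, an item that captures exactly the true overdoses: m1 = 0.10, m2 = 0.05. Variance = (10 + 3 + 20 + 3)/480 = 0.075, SE = 0.274, and power = Φ(0.693/0.274 − 1.645) = 0.81.

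Question 1 with s = 0.5 and r = 1: RR = 0.25 + 0.5 = 0.75, m1 = 0.20, m2 = 0.15. Variance = (5 + 3 + 6.67 + 3)/480 = 0.0368, SE = 0.192, and power = Φ(0.288/0.192 − 1.645) = 0.44.

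The same steps for the other cases give RR (power):

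| Change in other days | s = 0.10 | s = 0.20 | s = 0.30 | s = 0.50 |
|---|---|---|---|---|
| None (r = 1.0) | 0.95 (0.11) | 0.90 (0.18) | 0.85 (0.26) | 0.75 (0.44) |
| Fall 20% (r = 0.8) | 0.77 (0.63) | 0.74 (0.64) | 0.71 (0.66) | 0.65 (0.70) |
| Fall 30% (r = 0.7) | 0.68 (0.90) | 0.66 (0.86) | 0.64 (0.84) | 0.60 (0.82) |
| Fall 50% (r = 0.5) | 0.50 (>0.99) | 0.50 (>0.99) | 0.50 (0.99) | 0.50 (0.95) |

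The rate ratio is attenuated whenever the other days fall by less than overdoses do. Power drops below 0.81 in the first two rows and is above it in the last two, because question 1 has the larger count.

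**The narrower item under the same formula**

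If 75%, 50% or 25% of true overdoses receive medical assistance, the baseline mean is 0.075, 0.05 or 0.025. With RR 0.50 the power is 0.72, 0.59 or 0.39. At 50%, for example, variance = (20 + 3 + 40 + 3)/480 = 0.1375, SE = 0.371, and power = Φ(0.693/0.371 − 1.645) = 0.59. The 0.81 benchmark therefore does not describe the assisted item.

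**The case against.** Three stronger readings are tempting, and the documents do not support them.

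*That the item does not measure overdose.* It asks on how many days patients think they overdosed, and the broad wording explains that question. Non-fatal overdoses in followed-up patients are counted. Protocol 14.12 itself assigns non-fatal overdose to self-report on this form, and Protocol 10.2.11 cites an outside source for the overdose questions that cannot be checked here. Over-inclusive is the accurate description.

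*That it dilutes any real reduction.* This requires over-sedation days to respond less than overdoses. The trial also expects fewer days of illicit opioid use (Protocol 4.3.4), which could well lower over-sedation days too. If they fall in the same proportion there is no attenuation, and the larger count raises power.

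*That the assisted-overdose item should replace question 1.* That item misses overdoses that received no help, and it depends on care-seeking. IF includes harm-reduction counselling (Protocol 11.11) and marketing of ED treatment to patients (Protocol 11.10), and naloxone supply is tracked by period (SAP Table 20). IF could therefore change how often an overdose leads to medical help.

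It is also fair to say that the gap is partly covered. Table 35 shows both items by period, and SAP 8.4 lists deaths with relatedness to overdose. But those are safety summaries with no test. SAP 8.0 and Listing 9 exclude deaths found through the National Death Index, whereas SAP 3.3.5 includes them. What remains is the label, the lack of a modelled narrower measure and the dropped sources.

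**Conclusion.** The point stands in a limited form. SAP 7.6.2 item 2 gives the name overdose events to a self-reported count of days that is over-inclusive for non-fatal overdose and closed to fatal overdose. It departs without explanation from the four sources in Protocol 8.4 and 12.14.4. Taken alone, the result cannot support the hypothesis of fewer overdose events, whichever way it falls.

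The mismatch in sources and the loss of fatal overdoses follow from the texts and need no assumption. The size of any attenuation is unknown. In the illustration, a halving appears as anything from 0.50 to 0.95, depending on the share of over-sedation days and how they respond. Those figures rest on an assumed rate, effect, dispersion and significance level, and they are not estimates for this trial.

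The consequence is bounded. This is one of five secondary effectiveness outcomes, SAP 9.0 treats secondary findings as hypothesis-generating, and neither primary outcome is touched.

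**What to change.** Amend SAP 7.6.2 item 2 in three respects.

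1. Label the question 1 result *self-perceived overdose days (past 30 days)* and do not report it as overdose events.
2. Pre-specify a companion analysis that applies the same count model to the item on days with an opioid overdose needing medical assistance. Report both results together, with neither replacing the other.
3. Add fatal and record-confirmed overdoses within 30 days from the sources in Protocol 8.4, reported by evaluation period, or state that these sources are dropped and why. Make SAP 3.3.5, SAP 8.0 and Listing 9 agree on deaths found through the National Death Index.

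The first two changes need only SAP wording and one more model run, since the item is already collected and tabulated. The third uses searches that Protocol 10.2.11 and 14.12 already plan, plus rules to avoid counting one event twice. The companion analysis will have fewer counted days, will miss unassisted overdoses and may be affected by care-seeking that changes with IF. The report should say so.
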